## **8.4 Protocol Deviation Description**

Protocol deviations will be listed in the final study report.

## **8.5 Protocol Amendments**

Once the protocol has been approved by the IRB and Health Canada, any changes to the protocol will be documented in the form of an amendment. All amendments will be included in the final study report.

## **9 DATA COLLECTION AND STORAGE**

All data collection and record storage will be done in compliance with ICH GCP Guidelines and applicable local regulatory guidelines and with KGK standard operating procedures (SOPs).

## **10 ETHICAL ASPECTS OF THE STUDY**

This study will be conducted with the highest respect for the individual participants according to the protocol, the ethical principles that have their origin in the Declaration of Helsinki, and the ICH Harmonised Tripartite Guideline for GCP.

### **10.1 IRB Approval**

KGK Synergize Inc. will supply relevant documents for submission to an IRB for the protocol's review and approval. The following must be submitted to the IRB: This protocol, a copy of the informed consent form, and, if applicable, volunteer recruitment materials and/or advertisements and other documents required by all applicable laws and regulations. The IRB's written approval of the protocol and volunteer informed consent must be obtained before commencement of the study. The IRB approval must refer to the study by exact protocol title, number, and version date; identify versions of other documents (e.g., informed consent form) reviewed; and state the approval date.

KGK must adhere to all requirements stipulated by the IRB. This may include notification to the IRB regarding protocol amendments, updates to the informed consent form, recruitment materials intended for viewing by volunteers, local safety reporting requirements and submission of the investigator's annual/final status report to the IRB.

### **10.2 Volunteer Information and Informed Consent**

Written consent documents will embody the elements of informed consent as described in the declaration of Helsinki and the ICH Guidelines for GCP and will be in accordance with all applicable laws and regulations. The informed consent form describes the planned and permitted uses, transfers, and disclosures of the volunteer's personal and personal health information for purposes of conducting the study. The informed consent form further explains the nature of the study, its objectives, and potential risks and benefits, as well as the date informed consent is obtained. The informed consent form will detail the requirements of the volunteer and the fact that he or she is free to withdraw at any time without giving a reason and without prejudice to his or her further medical care. A properly executed informed consent document will be obtained from each subject prior to entering the study. The signed informed consent document will be maintained in the study file and a copy given to the subject.

### **10.3 Potential Risks and Procedures to Minimize Risk**

All potential risks are disclosed to study participants prior to their participation. The potential risks associated with this study include venipuncture and the associated risks. Risks associated with venipuncture include pain, bruising, and infection at the site. Alcohol swabs and proper venipuncture procedure will be followed to minimize the risk of infection.

## **11 QUALITY ASSURANCE AND QUALITY CONTROL**

### **11.1 Auditing**

All material used in clinical studies are subjected to quality control. Quality assurance audits may be performed by the sponsor or any health authority during the course of the study or after its completion.

The Investigator agrees to comply with the sponsor and regulatory requirements in terms of auditing of the study. This includes access to the source documents for source data verification.

### **11.2 Monitoring**

An initiation meeting in person or via conference call will be conducted by the sponsor. At this meeting, the protocol and logistical aspects of the study will be reviewed with the Investigator and all study staff.

The sponsor monitor may make site visits during the study and may inspect all case report forms, the clinical staff training and competency record and other documentation directly associated with the study. Source documents will be reviewed to ensure that all items have been completed and that the data provided are accurate and obtained in the manner specified in the protocol. The participant files will be reviewed to confirm that:

- Informed consent was obtained and documented;
- Enrolled participants fulfilled all inclusion criteria and did not meet any exclusion criteria;
- AE/SAE reporting has been performed as applicable;
- Study visits have been conducted as per protocol and information has been recorded in the appropriate place in the source document;
- The study product is being stored correctly and an accurate record of its dispensation to the study participants is being maintained (accountability).

Incorrect, inappropriate, or illegible entries in the participant files will be returned to the Investigator or designee for correction. No data disclosing the identity of participants will leave the study center. The Investigator and any designees will maintain confidentiality of all participant records.

The Investigator will permit trial-related monitoring, audits, IRB/IEC review, and regulatory inspections and will allow direct access to source data and documents for these purposes.

### **11.3 Data Management**

Data required for the analysis will be acquired from source documentation (including laboratory reports) and entered into a Microsoft Office Access database designed specifically for this study. All data points entered into the study database are source data verified.

High safety standards for the transfer and storage of study data are guaranteed by the use of technologies such as password protection, firewalls and periodic backup to protect stored data. Writing access to the system will be limited to authorized personnel.

All data including originals or copies of all case report forms, correspondence, study reports, and all source data is archived for a period not less than 25 years from the date of completion of the study in accordance with Health Canada regulatory requirements.

### **Study Report**

A draft study report is prepared by the test facility and written as per ICH E3 guidelines. The following information will be included, as appropriate, in the draft study report:

1. Introduction/objective
2. Investigational site location
3. Study reference number(s)
4. Test products
5. Study dates
6. Subject selection
7. Methods including any statistical analysis
8. Results
9. Discussion/conclusion
10. Authorized signatures

The test facility will finalize the study report upon receiving comments from Sponsor

## 13 APPENDICES

### 13.1 Appendix 1

### Schedule of Assessments

Procedures/assessments	Visit 1 Screening		Visit 2 Baseline 0-12 hour	Visit 3 24 hour		Visit 4 0-12 hour	Visit 5 24 hour End of study
	1 st study period		1 st study period	1 st study period		2 nd study period	2 nd study period
Informed Consent	X						
Review of Inclusion/Exclusion criteria	X		X				
Review of medical history/current health status	X		X			X	
Review of concomitant therapies	X		X	X		X	X
Review adverse events				X		X	X
Height*, weight, blood pressure and heart rate	X		X	X		X	X
Randomization			X				
Physical Exam			X				
Nutrition counselling	X						
Laboratory Tests				X			
Blood sample collection for CBC, electrolytes, HbA1c*, creatinine, eGFR, AST, ALT, and bilirubin analysis	X					X	X
Urine pregnancy test	X						
Blood samples: Pre-dose (t=0) and Post-dose (30 min, 1h, 2h, 3h, 4h, 5h, 6h, 8h, 10 h, 12 h) for L-Ascorbic Acid analysis			X			X	
Blood samples: 24 hours for L-Ascorbic Acid analysis				X			X
Pre-dose Urine sample for L-Ascorbic Acid analysis			X			X	
Post-dose urine samples: 0-2h, 2-4h, 4-8h, 8-12h post-dose L-Ascorbic Acid analysis			X			X	
Dispense urine collection kits for 8-24h urine collection: L-ascorbic acid			X			X	
Return post-dose urine sample collection: 12-24h post-dose L-Ascorbic Acid analysis				X			X
IP or Comparator Dispensed			X			X	
Breakfast, lunch, and dinner provided			X			X	
Study diary dispensed			X	X		X	
Study diary returned				X		X	X
24h-food record dispensed			X			X	
24h-food record returned				X			X
7-day food record dispensed	X			X			
7-day food record returned				X			

\* Will only be measured at screening visit (Visit 1)

## 13.2 Appendix 1a Time Points for Sampling

Blood Draw for Ascorbic Acid Measurement (Table 1A), Safety Parameters (Table 1B) and Urine Collection (Table 1C). One of two vials will be retained.

Table 1A. Time Points for Blood Draw – Ascorbic Acid Measurement Blue cells are vials that will be aliquoted from tubes in green cells													
		Visits 2 & 4										Visits 3 & 5	
Timing (Hour)		0 h	30 min	1 h	2 h	3 h	4 h	5 h	6 h	8 h	10 h	12 h	24 h
Number of Vacutainer tubes (8 mL/tube)		2	2	2	2	2	2	2	2	2	2	2	2
Total blood volume (mL)		16	16	16	16	16	16	16	16	16	16	16	16
Number of vials for Plasma		2	2	2	2	2	2	2	2	2	2	2	2
Number of cryovials for WBC		2	2	2	2	2	2	2	2	2	2	2	2

Table 1B. Time Points for Blood Draw – Safety Parameters					
Timing		Screening Visit 1		Visit 4 0 h	Visits 3 & 5 24 h
Number of vacutainer tubes		2 tubes (4mL/tube) 1 tube (5mL/tube)		1 tube (4mL/tube) 1 tube (5mL/tube)	1 tube (4mL/tube) 1 tube (5mL/tube)
Total volume (mL)		13 mL		9 mL	9 mL

Table 1C. Time Points for Urine Collection – Ascorbic Acid Measurement														
	Visits 2 & 4											Visits 3 & 5		
Hour	0 h	1 h	2 h	3 h	4 h	5 h	6 h	7 h	8 h	9 h	10 h	11 h	12 h	12 h → 24 h
Timing	Prior to Dosing	0-2 h Post-dose		2-4 h Post-dose		4-8 h Post-dose			8-12 h Post-dose			13-24 h post-dose		
Number of vials	2 Vials	2 Vials		2 Vials		2 Vials			2 Vials			2 Vials		

### 13.3 Appendix 2    Vitamin C Foods

For this study, we ask that you lower your consumption of foods containing high amounts of vitamin C during the study period.

Foods containing high amounts of vitamin C:

- Fruit Juices
- Veggie juices
- Fruits
- Fruit Based Snacks (Welch's Fruit Snacks, Fruit Roll-Ups, etc.)
- Kale
- Cauliflower
- Broccoli
- Cabbage
- Bell Peppers

### 13.4 Appendix 3 Meal Items low in Vitamin C for Meal Planning During the Study

BREAKFAST	LUNCH	DINNER

CEREALS
 

 RAISIN BRAN

 SHREDDED WHEAT

 UNPROCESSED BRAN

 HOMINY GRITS

 CREAM OF WHEAT

 
ENTREES
 

 SCRAMBLED EGGS

 HARD POACHED EGGS

 CHEDDAR CHEESE

 FRENCH TOAST

 SYRUP

 PLAIN YOGURT

 STRAWBERRY YOGURT

 
BREADS AND SPREADS
 

 BRAN MUFFIN

 GLAZED DOUGHNUT

 MINI BAGEL

 CREAM CHEESE

 WHITE TOAST

 WHEAT TOAST

 MARGARINE

 BUTTER

 HONEY

 PEANUT BUTTER

 
OTHER
 

 SUGAR SUBSTITUTES

 LOW-FAT CREAM CHEESE

 
BEVERAGES
 

 COFFEE

 DECAFFEINATED COFFEE

 TEA

 DECAFFEINATED TEA

 CREAM

	
APPETIZERS, SALADS, AND DRESSINGS
 

 CHICKEN NOODLE SOUP

 CREAM OF CHICKEN SOUP

 CROUTONS

 
ENTREES
 

 ESCALLOPED CHICKEN

 PORK CHOPS

 BROWN GRAVY

 GARLIC HERB PIZZA

 GRILLED CHEESE SANDWICH

 VANILLA YOGURT

 TUNA CHUNKS

 PLAIN YOGURT

 BLUEBERRY YOGURT

 
VEGETABLES AND STARCHES
 

 RICE ROYALE

 BLACK BEANS

 RICE

 PRETZELS

 
DESSERTS
 

 DIET JELLO

 CHOCOLATE CHIP COOKIE

 VANILLA ICE CREAM

 CHOCOLATE ICE CREAM

 SUGAR COOKIE

 
BREADS AND SPREADS
 

 WHITE BREAD

 MARGARINE, BUTTER

 WHEAT BREAD

 SALTINES

 SOUR CREAM

 PEANUT BUTTER

	
APPETIZERS, SALADS, AND DRESSINGS
 

 CHICKEN AND RICE SOUP

 COTTAGE CHEESE

 CROUTONS

 
ENTREES
 

 FRIED SHRIMP

 ROAST BEEF

 BROWN GRAVY

 MACARONI AND CHEESE

 CHEESEBURGER

 CHICKEN SALAD

 PLAIN YOGURT

 PEACH YOGURT

 
VEGETABLES AND STARCHES
 

 PINTO BEANS

 RICE

 
DESSERTS
 

 DIET JELLO

 VANILLA ICE CREAM

 ANGELFOOD CAKE

 
BREADS AND SPREADS
 

 MARGARINE

 BUTTER

 PEANUT BUTTER

 WHITE BREAD

 WHEAT BREAD


**MILK**

- WHOLE
- 2% FAT
- SKIM
- CHOCOLATE
- BUTTERMILK

**OTHER**

- MUSTARD
- MAYONNAISE
- SUGAR SUBSTITUTE
- RELISH

**BEVERAGES**

- COFFEE
- DECAFFEINATED COFFEE
- TEA
- DECAFFEINATED
- TEA
- ICED TEA
- CREAM

**BEVERAGES**

- COFFEE
- DECAFFEINATED COFFEE
- CREAM
- TEA
- DECAFFEINATED TEA
- ICED TEA

**EVENING SNACKS**

- PEANUT BUTTER CRACKERS
- GRAHAM CRACKERS
- CHOCOLATE CHIP COOKIE
- POPCORN
- GINGER ALE
- DIET COLA

### 13.5 Appendix 4

### Clinic Meal Choices

Please choose from the following items for each meal (V or X). You may drink as much water as you like.

#### Breakfast:

White Toast (1 slice)	
Wheat Toast (1 slice)	
Peanut Butter (1 tbsp.)	
Honey Nut Cheerios (1 cup)	
Shredded Wheat (1 cup)	
Scrambled Egg (1 cup)	
Hash Browns (1/2 cup)	
Coffee	
Tea	
Cream (1 tbsp.)	
Sugar (1 tsp)	

#### Lunch:

Minestrone Soup (1 regular)	
Chicken Noodle Soup (1 regular)	
Chili (1 regular)	
Crackers	
Dinner Roll (1 small roll)	
BLT Sandwich	
Ham & Swiss Sandwich	
Granola Bar (1 bar)	
Chocolate Chip Cookie (1 cookie)	
Jell-O Cup (1 pack)	
Coffee	
Tea	
Cream (1 tbsp.)	
Sugar (1 tsp)	
Ginger Ale (1 can)	
Coca Cola (1 can)	

#### Dinner:

Minestrone Soup (1 regular)	
Chicken Noodle Soup (1 regular)	
Chili (1 regular)	
Crackers	
Dinner Roll (1 small roll)	
Beef Lasagna	
Vegetarian Lasagna	
Granola Bar (1 bar)	
Chocolate Chip Cookie (1 cookie)	
Jell-O Cup (1 pack)	
Coffee	
Tea	
Cream (1 tbsp.)	
Sugar (1 tsp)	
Ginger Ale (1 can)	
Coca Cola (1 can)	

### 13.6 Appendix 5

### Randomization Schedule and Dispensing Log – 18 Participants Per Sex

#### 17MBHC Randomization Schedule and Dispensing Log

\*Ensure you select the appropriate Male or Female Randomization Log\*

MALES							
Randomization Number	Participant ID (ex. ABC 123)	Week 1	Date Dispensed	Initial	Week 2	Date Dispensed	Initial
7508		B			A		
7511		A			B		
7517		A			B		
7520		B			A		
7518		A			B		
7505		B			A		
7514		B			A		
7501		A			B		
7510		B			A		
7502		A			B		
7513		B			A		
7506		A			B		
7516		A			B		
7504		A			B		
7503		B			A		
7509		B			A		
7519		A			B		
7512		B			A		
7515		B			A		
7507		A			B		

Note: The last two randomization numbers from this list (randomization number 7515 and 7507) will not be used.

**17MBHC Randomization Schedule and Dispensing Log**

\*Ensure you select the appropriate Male or Female Randomization Log\*

FEMALES							
Randomization Number	Participant ID (ex. ABC 123)	Week 1	Date Dispensed	Initial	Week 2	Date Dispensed	Initial
7529		B			A		
7526		A			B		
7521		B			A		
7533		A			B		
7534		B			A		
7535		A			B		
7539		B			A		
7540		A			B		
7528		A			B		
7530		B			A		
7524		A			B		
7527		B			A		
7532		A			B		
7537		B			A		
7523		A			B		
7538		B			A		
7525		A			B		
7531		B			A		
7522		B			A		
7536		A			B		

Note: The last two randomization numbers from this list (randomization number 7522 and 7536) will not be used.

## 13.7 Appendix 6

## Laboratory Processing Flow Chart

### Blood Samples for Ascorbic Acid Analysis

#### Plasma

Wrap the red/green-top vacutainer tubes (sodium-heparin CPT™ vacutainer tube) in foil

Collect 8 mL of blood in two foil covered red/green-top vacutainer tubes

Invert the blood-filled vacutainer tube 8-10 times

Immediately Centrifuge the tubes for 20 minutes at 1500 RCF at 18-25°C

Pipette plasma from the vacutainers into 2 amber cryogenic vials (2 mL per tube)

Freeze immediately and store at -80°C

Deliver one cryogenic vial on dry ice to LifeLabs  
[REDACTED] and retain the second vial at KGK laboratory  
[REDACTED]

#### WBC

After plasma separation pipette the cell layer out of each vacutainer tube and place in a conical tube that is in an ice slurry.

Add PBS to the conical tube to bring volume to 15 mL and invert 5 times to mix the cells

Centrifuge the conical tubes for 15 minutes at 300 CRF at 4°C

Discard the supernatant without disturbing the cell pellet and resuspend cell pellet by gently vortexing the conical tube

Add PBS to the conical tube to bring volume to 10 mL and invert 5 times to mix the cells

Centrifuge the conical tubes for 10 minutes at 300 CRF at 4°C

[figure not shown]
Discard the supernatant without disturbing the cell pellet and resuspend cell pellet in PBS

Freeze immediately and store at -80°C

Deliver one cryogenic vial to Mount Sinai laboratory  
[REDACTED] and retain the second vial at KGK laboratory  
[REDACTED]

### 13.8 Urine Samples for Ascorbic Acid Analysis

## 24 h Post-Dose

Record the total volume of the urine from 2-4 h post-dose

Agitate for ensure homogeneity of urine collection

Aliquot 8 mL of the urine into amber tube

Centrifuge the amber tube for 20 minutes at 1000 X g rpm at 4°C

Aliquot 2 mL of the supernatant in two amber cryogenic vials and label as pre-dose

Store at -80°C immediately

*Deliver one cryogenic vial to Mount Sinai laboratory  
( [REDACTED] )  
and retain the second vial at KGK laboratory  
( [REDACTED] )*

## 4-8 h Post-Dose

Record the total volume of the urine from 4-8 h post-dose

Agitate for ensure homogeneity of urine collection

Aliquot 8 mL of the urine into amber tube

Centrifuge the amber tube for 20 minutes at 1000 X g rpm at 4°C

Aliquot 2 mL of the supernatant in two amber cryogenic vials and label as pre-dose

[figure not shown]

Store at -80°C immediately

[figure not shown]
*Deliver one cryogenic vial to Mount Sinai laboratory  
( [REDACTED] )  
and retain the second vial at KGK laboratory  
( [REDACTED] )*

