# 6 STUDY ASSESSMENTS

See Appendix 1 for the schedule of assessments and procedures, and Appendix 1a for time points for blood and urine sampling:

- Table 1A: A total of twelve (12) time points for blood sampling including baseline prior to dosing at 0h, and 0.5, 1, 2, 3, 4, 5, 6, 8, 10, 12 and 24 h post dosing for ascorbic acid analysis.
- Table 1B: A total of four time points for blood safety parameters.
- Table 1C: A total of six time points for urine ascorbic acid.

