## **6.3 Visit 2 – Baseline: Clinic Day 1 (Test Period 1, 8h In-Clinic Day)**

Eligible participants will return to the clinic after fasting for 12 hours (only water is allowed) for baseline assessments.

Baseline assessments include:

- Reviewing of concomitant therapies and current health status
- Physical exam
- Assessing of inclusion and exclusion criteria
- Collecting 7-day food record and reviewing dietary compliance
- Randomizing eligible participants

- Recording weight and BMI
- Recording seated resting blood pressure and heart rate
- Blood collection (plasma and WBC) for pre-dose baseline (0h) analysis of L-ascorbic acid
- Pre-dose urine collection (baseline 0h) and total urine volume will be recorded and a sample for L-ascorbic acid analysis will be retained
- Following randomization and collection of pre-dose samples, Investigational product administration with 250 mL of room temperature water and recording of consumption time. Participants who receive the gummies will be instructed to chew gummies thoroughly before swallowing. Water will be permitted ad libitum 1-hour after dosing.
- Participants will be instructed to avoid reclining for 2 hours after dosing.
- Blood collection (plasma and WBC) for post-dose analysis of L-ascorbic acid at 30min, 1h, 2h, 3h, 4h, 5h, 6h, 8h, 10h and 12h post-dose
- Urine collection between 0-2h post-dose and total volume will be recorded.
- Sample of 0-2h post dose urine will be retained for L-ascorbic acid analysis
- Urine collection between 2-4h post-dose and total volume will be recorded.
- Sample of 2-4h post dose urine will be retained for L-ascorbic acid analysis
- Urine collection between 4-8h post-dose and total volume will be recorded
- Sample of 4-8h post dose urine will be retained for L-ascorbic acid analysis
- Urine collection between 8-12h post-dose and total volume will be recorded
- Sample of 8-12h post dose urine will be retained for L-ascorbic acid analysis
- Recording of adverse events

Standardized meals devoid of vitamin C containing products will be provided to participants in the clinic (Refer to appendix 4). The following meals will be provided at the clinic: Breakfast after the 2h blood sampling, lunch after the 5h blood sampling, and supper between the 6h and 12h sampling. All food items and quantities consumed will be recorded by clinic staff for each individual participant.

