4. At the end of each collection period urine will be agitated to ensure homogeneity of the collected urine sample and 8 mL sample will be transferred into a opaque tube.
5. The opaque tube will be centrifuged at 1000 x g for 20 minutes at 4°C.
6. 2 mL aliquot of the supernatant will be transferred into two amber cryovials and stored at -80°C.
7. One cryovial will be delivered to Mount Sinai Laboratory for analysis and one vials will be retained at KGK.
8. Throughout this process the sample will be protected from light.

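### The flow charts for the 2-4 h and 4-8 h post-dose urine collections tell staff to label the vials as pre-dose, an internal inconsistency of minor severity confined to informational urine data

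*Combined protocol and SAP*

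**What the plan says.** Section 6.9 refers the reader to Appendix 6 for the sample-processing flow chart. Two of the urine charts under Section 13.8 can be read in full.

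- The first opens with "Record the total volume of the urine from 2-4 h post-dose".
- The second opens with "Record the total volume of the urine from 4-8 h post-dose".
- Both then give the same aliquoting step: "Aliquot 2 mL of the supernatant in two amber cryogenic vials and label as pre-dose".

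The body of the protocol treats these as three different samples. At Visit 2 (Section 6.3) there is a sample before dosing: "Pre-dose urine collection (baseline 0h) and total urine volume will be recorded and a sample for L-ascorbic acid analysis will be retained". Separately, "Sample of 2-4h post dose urine will be retained for L-ascorbic acid analysis" and "Sample of 4-8h post dose urine will be retained for L-ascorbic acid analysis". Section 6.6 repeats the scheme for the second period, and Section 6.9 (Urine Collection) and Table 1C of Appendix 1a list the same intervals. Section 6 gives the number per period: "A total of six time points for urine ascorbic acid".

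Each collection yields two vials: "One cryovial will be delivered to Mount Sinai Laboratory for analysis and one vials will be retained at KGK".

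Section 6.9 also says that samples will be coded alphanumerically and that those doing the assays will not know the participant or the product. Section 8.3 describes the urine measurements as collected for information only. Its one stated use for them is line graphs of individual and mean concentrations over 24 h.

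**The concern.** A flow chart is what staff work from at the bench, so a wrong label step there can pass straight onto vials. Pre-dose is also not an empty category in this trial, because a true 0 h urine sample is taken in each period. A 2-4 h or 4-8 h vial marked pre-dose would therefore share its label with a genuine sample.

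At stake is whether urine concentrations can be placed at the right time. If the label were what the external laboratory and the database relied on, the 2-4 h and 4-8 h values would be entered at 0 h, and the graphs would have nothing in those two intervals. The retained vial would offer no independent check, because a single instruction labels both vials of a collection.

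**Working it through.** No power, alpha or sample-size figure is involved, and the plan states no figure to reproduce. The check compares texts and then counts vials.

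**Step 1. Set the texts side by side.**

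| Collection | Status in Sections 6.3, 6.6, 6.9 and Table 1C | Label in the Section 13.8 chart |
|---|---|---|
| 0 h | pre-dose | chart not readable in the text available |
| 0-2 h | post-dose | chart not readable |
| 2-4 h | post-dose | pre-dose |
| 4-8 h | post-dose | pre-dose |
| 8-12 h | post-dose | heading only |
| 12-24 h | post-dose | heading only |

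Two charts are contradicted by their own volume step and by the body text. The others cannot be checked here, and no claim is made about them. The first readable chart is headed 24 h Post-Dose; since its volume step says 2-4 h, this is most likely 2-4 h with a lost hyphen and is not counted as a second error.

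**Step 2. Look for a correction elsewhere.** The numbered urine-processing steps in Section 6.9 give no label wording. They also list the post-dose collections as 0-4 h, 4-8 h and 8-24 h, which differs from the five intervals used elsewhere, so they cannot serve as a check on the charts. No other section states what the urine labels should say.

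**Step 3. Share of time points affected, per period.**
- Urine time points: 6, of which 1 is pre-dose and 5 are post-dose (Section 6; Table 1C).
- Post-dose intervals with the wrong label: 2 of 5 = 40%.
- Time points labelled pre-dose as intended: 1 of 6, or 1 x 2 = 2 vials.
- Time points labelled pre-dose as written: at least 3 of 6, or 3 x 2 = 6 vials, assuming the 0 h vials are labelled pre-dose.

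**Step 4. Number of vials.** Analysed vials = participants x 2 periods x 2 intervals x 1 vial. The total including retained vials is twice that. Participant numbers are from Section 3.

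| Participants with both periods | Analysed | With retained vials |
|---|---|---|
| 30 (planned completers) | 30 x 2 x 2 = 120 | 240 |
| 36 (all randomized) | 36 x 2 x 2 = 144 | 288 |

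**Step 5. Trace the consequence.** For these vials to be plotted at the wrong time, two things must both hold: staff follow the label step literally, and the label, rather than the sample code or another record, sets the time point. The documents settle neither. If both hold, each participant's urine graph in each period would have three values competing for 0 h and none for 2-4 h or 4-8 h.

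**The case against.** The strongest reply is that this is a copied line that would be caught. Each chart names its own post-dose interval in the volume step, and the second is headed with it. Volumes are recorded for every collection period, and staff would already have 0 h vials from the same participant. Literal compliance across all participants and both periods is a worst case. This stands as an argument about likelihood, and it is why the consequence is put conditionally. It does not make the instruction right.

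A reader might infer three stronger conclusions. The documents do not support them.

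- *That the link between sample and time is lost beyond repair.* Section 6.9 provides for an alphanumeric code without saying what it contains. It may carry the time point or it may not, so neither loss nor preservation can be asserted.
- *That a urine baseline would be inflated or an excretion analysis damaged.* Section 8.3 specifies no urine baseline adjustment, no cumulative excretion and no urine hypothesis test. Concentration graphs are the only planned use.
- *That a main result is at risk.* The primary variable is plasma Cmax, tested against 37 µM for each product. Plasma vials are handled under a separate chart that does not contain this label step. The safety analyses do not use urine ascorbic acid.

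Nor is this a disputed design choice. The design of the urine sampling is clear in the body of the protocol; the appendix fails to match it.

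**Conclusion.** The point holds as an internal inconsistency of minor severity. Two bench instructions are wrong as written, and no other text corrects them. That rests on the wording alone and needs no assumption.

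The size is conditional. If the charts are followed literally and the vial label determines the time point, 40% of the post-dose urine intervals in each period would be recorded as pre-dose: 120 analysed vials for 30 completers, with 144 as the upper figure if all 36 randomized participants complete both periods. The urine concentration-time graphs would then be wrong. Because the urine data are informational, the damage stops there; the plasma Cmax test, the action standard built on it and the safety analyses are untouched.

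**What to change.** In Section 13.8 of Appendix 6, change the label step on each post-dose urine chart to that chart's own collection interval and study period, and reserve pre-dose for the 0 h collection. Check the same line on the 0-2 h, 8-12 h and 12-24 h charts, which could not be read here. It would also help to add one sentence to Section 6.9 saying whether the alphanumeric code identifies the period and time point.

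The cost is a wording correction before the first participant is dosed. It changes no procedure, sample or analysis and has no evident downside.
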